5.2 Institutional Review Board

Institutional Review Boards and Research Ethics Boards must be constituted and their authority delegated through the institution's normal process of governance according to applicable State and Federal requirements for each participating location. Each participating institution must provide for the review and approval of this protocol and the associated informed consent documents and recruitment materials by an appropriate IRB registered with the Office for Human Research Protections (OHRP). The protocol will be submitted for approval to the appropriate IRB for each study site. The study will not commence at any site until written approval for investigational product release and approval to enroll is obtained from ADCS Regulatory Affairs.

The investigator must obtain approval from the IRB for all protocol amendments and, when warranted, changes to the informed consent document. Protocol and informed consent form

amendments can be made only with the prior approval of the ADCS and Sponsor. The investigator may not implement any protocol deviation except where necessary to eliminate an immediate hazard to study participants, or when change(s) involve only logistical or administrative aspects of the trial, i.e., change of monitor(s) or telephone number(s) (ICH 4.5.2). The investigator shall notify the IRB of deviations from the protocol or serious adverse events occurring at the site, in accordance with local procedures.

5.3 Informed Consent and HIPAA Compliance

No study-specific procedure will be undertaken on an individual participant until that participant or the participant's LAR has given written informed consent to take part in the study. The study partner must also participate in the consenting process.

It will be made clear to each potential participant, their LAR if applicable, and study partner that informed consent may be withdrawn at any time without needing to give a reason and that such withdrawal will not compromise the relationship between the participant and the Investigator nor the participant's future treatment.

Informed consent will be obtained in accordance with US 21 CFR 50.25 and ICH Good Clinical Practice. Applicable HIPAA privacy notifications will be implemented and HIPAA authorizations signed before protocol procedures are carried out. Information should be given in both oral and written form.

Consent forms must be in a language fully comprehensible to the prospective participants and/or their LARs, and study partners, and ample opportunity must be given to inquire about the details of the study. Prior to a participant's participation in the trial, the written informed consent form should be signed and personally dated by the participant or by the participant's LAR, and by the person who conducted the informed consent discussion. Participants or their LAR must be provided a copy of the signed ICF. Study partners may also be required to sign the informed consent prior to study participation at the discretion of the responsible IRB reviewing this research.

The consent for storage will include consent to access stored data, biological samples, and imaging data for secondary analyses. Consent forms will specify that DNA and biomarker samples are for research purposes only; the tests on the DNA and biomarker samples are not diagnostic in nature and participants will not receive results. MRI scan findings of clinical significance, determined by the site radiologist, can be shared with participants per site clinician discretion.

5.4 Participant Confidentiality | HIPAA

Information about study participants will be kept confidential and managed according to the requirements of HIPAA. Those regulations require a signed participant HIPAA Authorization informing the participant of the following:

- What protected health information (PHI) will be collected from participants in this study
- Who will have access to that information and why

- Who will use or disclose that information
- The rights of a research participant to revoke their authorization for use of their PHI

In the event that a participant revokes authorization to collect or use PHI, the investigator, by regulation, retains the ability to use all information collected prior to the revocation of participant authorization. Each site PI, under the guidance of his/her IRB, is responsible for ensuring that all applicable HIPAA regulations and state laws are met.

5.5 Potential Risks and Benefits Associated with this Study

5.5.1 Potential Risks

Risks associated with study participation are the potential for adverse reactions to the study medication (see Section 1.7.1), concomitant medications, invasive study assessments like blood draws and lumbar puncture, and risks related to the process of undergoing brain MRI scans and neuropsychological testing.

5.5.2 Potential Benefits

Participants in this study may experience an improvement in their AD symptoms, even though such improvement cannot be predicted with any surety. This study is expected to benefit the AD community by furthering the development of a new therapy and providing more information to those studying potential treatments for AD.

6 STUDY DRUG

6.1 Study Medication

The double-blind phase medication will be presented as one of the following:

- BHV-4157, 1 or 2 capsules (size 1) of 140 mg each, depending on assigned dose, and
- 1 or 2 capsules of matching Placebo

The Open-Label Extension phase medication will be:

BHV-4157, 1 or 2 capsules (size 1) of 140 mg each

[figure not shown]
The study medication capsule should not be opened.

[figure not shown]
The study medication will be securely stored at the study site in accordance with the conditions specified on the label, separately from other drugs. The study medication may not be used for any purpose other than this study.

6.3 CCI

6.4 Missed Doses

If a participant misses a dose of study drug and remembers within the same calendar day, the dose may be taken. If a participant misses a dose of study drug and does not remember until the next calendar day, the dose will be skipped (i.e., should not be made up) and dosing resumed at the normal dosing time for that calendar day.

6.5 Coding and Packing

Assignment of study medication kits to treatment groups will be done with an allocation ratio of 1:1 by a computer generated random sequence.

The study medication will be packaged in bottles. Each bottle will contain 35 capsules. An appropriate number of bottles (to provide study drug between visits) will be provided to the participant at each study visit (see Appendix 1 for Schedule of Study Visits).

Note: Each participant completing this study will take the study drug for 47 to 49 weeks in the double-blind phase, depending on scheduling of the End of Treatment Visit (week 48 ± 7 days) and an additional 47-49 weeks if they continue in the Open-Label Extension phase.

Note: If absolutely necessary, treatment duration may be longer due to the COVID-19 pandemic as detailed in the Schedule of Assessments and Events in Appendix 1. Under these circumstances, the sponsor medical monitor (or designee) should be consulted by the site investigator (or designee).

6.6 Blinding

This is a double-blind placebo-controlled trial. Treatments will be blinded to the participants and study personnel throughout the double-blind phase. Treatment blind will be maintained by use of matching placebo medication. In order to minimize unnecessary analysis of placebo blood PK samples, the bioanalytical scientist will be unblinded to treatment prior to unblinding

for the primary endpoint. Results of the blood concentration assay will be kept secure until database lock and unblinding for the primary endpoint.

Only in the case of an emergency, when knowledge of whether the participant has received the investigational product is essential for the clinical management or welfare of the participant, may the Investigator unblind a participant's treatment assignment. Procedures for emergency unblinding are initiated by contacting the ADCS Medical Monitor.

The interim analysis will be carried out by the unblinded safety biostatistics team and the report will be prepared for the DSMB. The DSMB will review all data pertaining to the column and will be unblinded. The DSMB will convey to the Study Steering Committee (SSC) whether or not the stopping criteria have been met.

The Study Steering Committee (SSC) that is overseeing the trial will receive the recommendation of the DSMB and have full access to data summaries provided to the DSMB. See Section 15 and the SSC Charter for additional details.

All participants entering the Open-Label Extension phase will not be blinded and will be on active treatment.

6.7 Randomization and Medication Ordering System

A stratified permuted block randomization procedure will be used with screening MMSE [moderate AD: 14 to 19; mild AD: 20 to 24] and Site as stratification factors.

The Investigator will use the ADCS EDC system to enter screening information on each participant. For those participants who qualify, the system will issue a medication kit number.

Participants will be randomized at the baseline visit, after screening is completed and it is determined that the participant is eligible for the study.

6.8 Labeling

Labels will be in accordance with all applicable regulatory requirements for the labeling of active pharmaceutical ingredients and with Annex 13 of GMP. Labels will contain the drug name, protocol number, date of manufacture, storage conditions and a caution statement that the drug is for clinical investigational use only.

6.9 Drug Accountability

The Investigator or his/her designated representatives will dispense study drug only to participants randomized to treatment in the study.

The Investigator (or, as appropriate, pharmacist/individual who is designated by the Investigator/institution) must maintain records of the delivery of the study medication to the trial site, the inventory at the site, the use by each participant, and the return to the drug distributor unless they are able to destroy on site.

At each visit, participants and their study partners should bring in all unused drug and empty or partially full containers. After the drug has been reviewed by the monitor, each site will destroy all unused study medication and empty or partially full containers collected from each participant, or return the study medication and containers to the drug distributor if they are unable to destroy on site.

If the study site needs to send drug overnight via certified and tracked courier where possible, and this is acceptable to the institution because a visit is absolutely not possible to be completed due to the COVID-19 pandemic, this is permissible per study. The sponsor should be consulted prior to shipping drug.

7 PARTICIPANT SELECTION AND CONCOMITANT MEDICATIONS

7.1 Inclusion Criteria

Participants must meet all of the following inclusion criteria to be eligible for enrollment:

- Age 50 to 85 (inclusive) at screening.
- 2. Diagnosed with probable Alzheimer's disease dementia: Core clinical criteria in accordance with NIA/Alzheimer's Association Guidelines (see Appendix II).
- Living in the community (includes assisted living facilities, but excludes long-term care nursing facilities).
- Ambulatory, or able to walk with an assistive device, such as a cane or walker.
- Participants must have a study partner who has frequent interaction with them (approximately >3-4 times per week), will be present for all clinic visits, and can assist in compliance with study procedures.
- 6. Female patients must be post-menopausal for at least 2 consecutive years or surgically sterile (bilateral tubal ligation, hysterectomy or bilateral oophorectomy) for at least 6 months prior to screening.
- A modified Hachinski score of 4 or less at screening.
- An MMSE score of 14 to 24, inclusive, at screening.
- A brain MRI scan within 6 months of screening consistent with a diagnosis of Alzheimer's disease.
- 10. Body mass index (BMI) \leq 40 kg/m² at screening.
- 11. Participants should be treated with a stable dosage regimen of FDA-approved AD medications (acetylcholinesterase inhibitors (AchEI) and/or memantine) for at least 3

months prior to screening. Participants should be expected to remain on a stable dosage regimen of these medications for the duration of the trial. The AD medication dose may be changed during the Open-Label Extension phase if needed, but it is preferred to wait until the Extension Phase Week 12 visit if possible.

- a. Participants who are not being treated with FDA-approved AD medications at the time of screening, because they have contraindications to these medications, or because they have previously failed treatment with these medications, are also eligible for inclusion, if it is expected that they will not be treated with these medications for the duration of the trial.
- 12. Ability (patients and their study partners) to read, speak and understand English or Spanish to ensure compliance with cognitive testing and study visit procedures.
- 13. Provision of informed consent from the participant (or the participant's legally authorized representative (LAR) if unable to provide consent) and the study partner.

7.2 Exclusion Criteria

Patients meeting any of the following criteria must not be included in the study:

- History of brain amyloid imaging (e.g., Amyloid Positron Emission Tomography scan) or cerebrospinal fluid results (e.g., based on tau and amyloid concentrations) that are not consistent with amyloidopathy or Alzheimer's disease. However, such tests may be repeated in order to determine eligibility, if discussed and approved by the Medical Monitor.
- Use of prohibited medications as defined in Section 7.4.2.
- Contraindication to MRI, including but not limited to:
 - a. Clinical history or examination finding that, would pose a potential hazard for conducting an MRI, in the judgment of the principal investigator.
 - b. Implant devices not compatible in the magnetic resonance environment, such as; AICDs; cochlear implants; cerebral aneurysm clips; implanted infusion pumps; implanted nerve stimulators; metallic splinters in the eye; other magnetic, electronic, or mechanical implants. Pacemakers are permitted only if labeled as conditional cardiac implantable electronic devices (CIEDs), have been approved for MRI use by the FDA, verified by the pacemaker's manufacturer as approved for MRI use, and determined to be suitable by the site's radiologist and principal investigator.
- Current serious or unstable illness including cardiovascular, hepatic, renal, gastroenterologic, respiratory, endocrinologic, neurologic, psychiatric, immunologic, or

hematologic disease or other conditions that, in the investigator's or sponsor's opinion, could interfere with the interpretation of safety and assessment of efficacy in this study.

- Hepatic impairment defined as Child-Pugh class of A or more severe liver impairment.
- Alanine aminotransferase (ALT/SGPT) values >1.5X the upper limit of normal (ULN) of the performing laboratory, aspartate aminotransferase (AST/SGOT) values >1.5X ULN, or total bilirubin values >1X ULN (participants with Gilbert's syndrome are allowed in the study).
- Other neurodegenerative diseases and causes of dementias, including Parkinson's disease and Huntington's disease, vascular dementia, CJD (Creutzfeldt-Jakob disease), LBD (Lewy Body dementia), PSP (Progressive Supranuclear Palsy), AIDS (Acquired Immunodeficiency Syndrome), or NPH (normal pressure hydrocephalus).
- 8. Brain MRI at screening shows evidence of infection, tumor, cortical infarction, extensive white matter disease (Fazekas score > 2), or multiple lacunes in prefrontal or critical memory regions; inconclusive findings may be subject to review by the ADCS Imaging Core.
- History of a major depressive episode within the past 6 months of screening.
- History of schizophrenia diagnosis.
- History of bipolar disorder.
- History of seizures within 2 years of screening.
- History of alcohol abuse or dependence or drug abuse in the past 5 years.
- Insulin-dependent diabetes or uncontrolled diabetes with HbA1c value >8.0 %.
- Hepatitis B, C, or HIV infection.
- Clinically significant laboratory abnormalities that may influence study assessments as determined by the investigator.
- Untreated or insufficiently treated hypothyroidism, vitamin B12 or folate deficiency.
- 18. ECG obtained during screening that, in the opinion of the investigator, is clinically significant with regard to the participant's participation in the study. Corrected QT interval (QTcF) must be evaluated using Fridericia's formula, and must not exceed 480 msec.
- 19. Cancer or a malignant tumor within the past 3 years, except patients who underwent potentially curative therapy with no evidence of recurrence for >3 years. Patients with stable prostate cancer or non-melanoma skin cancers are not excluded.

- 20. Participation in another clinical trial for an investigational agent and having taken at least one dose of study medication, unless confirmed as having been on placebo, within 12 weeks prior to screening. The end of a previous investigational trial is defined as the date of the last dose of an investigational agent.
- Having received riluzole for more than 4 weeks prior to screening or with known tolerability difficulties to riluzole.

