7.4 Other Concomitant Medication

7.4.1 Permitted Concomitant Medications

The following concomitant medications are permitted:

- Medical foods and soy-based supplements, except as described in Section 7.4.2.
- Food supplements in general
- Vitamins in general
- Non-sedating antihistamines

The patient's condition must be stable while on the prescribed medications:

- Antidepressants starting at least two months prior to screening except the prohibited medications as described in Section 7.4.2.
- Beta-blockers used for cardiovascular reasons starting at least 2 months prior to screening

The following concomitant medications are permitted on an intermittent basis.

- Short to medium-acting benzodiazepines (estazolam, lorazepam, midazolam, oxazepam, temazepam, triazolam, alprazolam) taken no more than twice weekly
- Ramelteon (up to 8 mg), eszopiclone (up to 2 mg), zaleplon (up to 5 mg) or zolpidem tartrate (≤6.25 mg CR and ≤10 mg tablet) taken no more than twice weekly

- Sedating anti-allergy medications (e.g. diphenhydramine) taken no more than twice weekly
- Low dose anticonvulsant drugs used for non-epileptic indications which have been started and have been stable for at least 2 months prior to screening. Depakote 250 mg, Gabapentin 300 mg, Oxcarbazepine 600 mg, Pregabalin 100 mg, Lamotrigine 75 mg)

Any concomitant medications must be recorded in the eCRF, noting the name of medication, the dose, duration, and indication. However, any of these permitted concomitant medications used on an intermittent basis should not be taken less than 12 hours prior to any scheduled visits that include any cognitive tests.

7.4.2 Prohibited Concomitant Medications for double-blind phase but conditional for Open-Label Extension phase

The following concomitant medications are not permitted from screening through the end of the Randomized Double-Blind phase of the study. However, they are allowed per investigator judgement for the Open-Label Extension phase unless otherwise noted in 7.4.3.

- Tricyclic antidepressants (e.g. amitriptyline, amoxapine, clomipramine, desipramine, doxepin, imipramine, nortriptyline, protriptyline, trimipramine)
- Monoamine oxidase inhibitors (e.g. isocarboxazid, phenelzine, tranylcypromine, selegiline, rasagiline)
- Long-acting benzodiazepines
- Conventional and atypical antipsychotics (EXCEPT ≤ 50 mg/d of quetiapine and ≤ 0.5 mg/d of risperidone)
- Mood-stabilizing psychotropic agents (e.g. lithium salts)

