- Prescription sedatives (e.g. barbiturates, methaqualone, meprobamate; EXCEPT ramelteon, eszopiclone, zaleplon and zolpidem tartrate under the condition described in Section 7.4.1.
- Psychostimulants (e.g. amphetamines, modafinil-related compounds like armodafinil)
- Dopamine agonists (e.g. apomorphine, pramipexole, ropinirole, rotigotine)
- Anticholinergics (e.g. benztropine mesylate, trihexyphenidyl HCL; EXCEPT inhaled ipratropium, inhaled tiotropium, oxybutynin, darifenacin, trospium, solifenacin and tolterodine)
- Anticonvulsant medications used to treat seizures or epilepsy which interfere with cognitive function or whose usage has not been stable for 6 months or longer (EXCEPT gabapentin at ≤ 300 mg QD for indications other than seizures)
- Chronic or regular use of opiate analgesics (e.g. morphine, codeine, hydromorphone, hydrocodone, meperidine, oxycodone)
- Immunosuppressive medications EXCEPT inhaled, topical, intra-nasal steroids, and low dose methotrexate for rheumatoid arthritis or psoriasis)
- Chemotherapeutic agents for malignancies
- Medical or recreational marijuana
- Glutamatergic agents (EXCEPT memantine)
- Hepatotoxic drugs (e.g. allopurinol, methyldopa, sulfasalazine) which may increase the

- risk for hepatoxicity
- Axona® and Souvenaid® (EXCEPT when patients are using Axona® or Souvenaid® at the time of screening and continued use is advised by treating physician or Principal Investigator and is expected to continue throughout the study)

Participants who are actively being treated with low dose acetylsalicylic acid (ASA) may undergo lumbar puncture, at the discretion of the investigator. Participants who are actively being treated with dual antiplatelet therapy or with any anticoagulation medications (e.g. heparin, warfarin, thrombin inhibitors, Factor Xa inhibitors) should not undergo lumbar puncture. Platelet counts should be >100,000, and PTT and INR levels checked and in normal range before the lumbar puncture is performed. The ADCS Medical Monitor should be contacted if there are any questions.

If, during the clinical study, the administration of a non-permitted concomitant medication becomes necessary, the Medical Monitor must be contacted to determine if the participant needs to be prematurely discontinued from active treatment (see Section 10).

7.4.3 Prohibited Medications, both in double blind and Open-label extension phases.

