The following concomitant medications are neither permitted in the double blind nor the openlabel extension phase of the Study:

 Hepatotoxic drugs (e.g., allopurinol, methyldopa, sulfasalazine) which may increase the risk for hepatoxicity

 Sensitive and moderately sensitive substrates of the CYP2B6, CYP2C8, CYP2C9, and CYP2C19 enzymes (please see the table below).

Enzyme	Sensitive Substrates	Moderately Sensitive Substrates
CYP2B6	Bupropion	efavirenz
CYP2C8	Repaglinide	montelukast, pioglitazone, rosiglitazone
CYP2C9	Celecoxib	glimepiride, phenytoin, tolbutamide, warfarin
CYP2C19	S-mephenytoin, omeprazole	diazepam, lansoprazole, rabeprazole, voriconazole

The following medications are prohibited at least 14 days prior to randomization or 5 half-lives (whichever is longer) prior to randomization, and during the double-blind and Open-Label Extension phases of the study, due to the potential for drug interactions:

- Strong to moderate CYP1A2 inhibitors, such as amiodarone, cimetidine, and ciprofloxacin which may increase the risk of riluzole-associated adverse events (See Appendix III for detailed medication listing)
- Chronic use of strong to moderate CYP1A2 inducers, such as carbamazepine, modafinil
 and omeprazole, which may result in decreased efficacy (See Appendix III for detailed
 medication listing)

[figure not shown]

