 - o If a participant has had an MRI within 6 months of screening (i.e., within 6 months from the date of informed consent) but the MRI does not follow the study-specific imaging protocol, that MRI can be used to help determine eligibility; however, another MRI must be performed per the imaging protocol, and must occur as close to, and prior to, the baseline visit, after all other eligibility criteria have been confirmed.
- Lumbar puncture*
- Post lumbar puncture safety telephone follow-up (1 to 3 days after lumbar puncture)
- Sheehan Suicidality Tracking Scale

*NOTE: Participants who have consented to participate in the CSF sub-study should undergo a lumbar puncture to obtain samples of CSF no more than 14 days prior to their first dose of study

drug at baseline. The participant's vitals should be assessed before and after the procedure, or per standard local practice. INR, PT, PTT and platelets should be assessed at the site's local laboratory at least 24 hours, and within normal range, prior to the lumbar puncture. The lumbar puncture should be done after the MRI scan if performed on the same day. If the lumbar puncture is performed on a separate day from the MRI and occurs before the MRI, then there must be at least a 3-day window between the lumbar puncture and the MRI. If the lumbar puncture is performed on a separate day from the MRI and occurs after the MRI, then there is no window (waiting period) between the MRI and lumbar puncture. Both the lumbar puncture and vMRI should occur after all other eligibility criteria have been confirmed.

Following completion of all screening assessments, results for participants who meet all inclusion and none of the exclusion criteria will be submitted via the ADCS EDC for central confirmation of eligibility. If confirmed to be eligible, permission to randomize will be issued and the participant may be randomized.

Randomization must occur at the baseline visit; otherwise, the participant will be considered a screen failure.

Re-screening

A single full re-screen (re-consent participant, assign new Participant ID and perform all screening assessments) may be conducted more than 14 days after the last assessment of a screening failure.

If the participant is failed again at re-screening, further re-screening and its minimum interval from the previous one, may be done if the PI and Central Review Medical Monitor are in agreement to do so.

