8.1.2 Baseline (Week 0)

At baseline, eligible participants will be randomized into the study. Each will undergo the following procedures prior to first dose of study medication:

- Verification of Inclusion/Exclusion criteria
- Randomization in EDC
- Physical exam
- Vital signs (sitting blood pressure, pulse, temperature, respiration rate)
- Weight
- Documentation of concomitant treatment
- Documentation of adverse events. Adverse events that occur prior to initiation of study drug will be documented as medical history.

- Blood samples for:
 - Safety laboratory tests (hematology and serum chemistry, as listed in Section 8.2).
 - Pharmacokinetics in plasma
 - Biomarker/banking
- Urinalysis (see Section 8.2)
- Sheehan Suicidality Tracking Scale
- ADAS-Cog 11
- CDR-SOB
- NPI
- ADCS-ADL
- Neuropsychological Test Battery
 - Craft Story 21 Recall (Immediate and Delayed)
 - Benson Complex Figure
 - Multilingual Naming Test (MINT)
 - Letter & Category Fluency
 - Trail Making Test A&B
 - Number Span Test
- MMSE
- Montreal Cognitive Assessment (MoCA)
- Research Satisfaction Survey

First dose of study medication will be given in the clinic at any time after completion of all of the above.

At this visit, all participants will receive a supply of study drug with instructions on how to take it. Participants will be given an appointment to return at week 4 ± 7 days).

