18.3 APPENDIX III – CYP INHIBITORS AND INDUCERS OF INTEREST

CYP1A2 Potent and Moderate Inhibitors

Amiodarone

Artemisinin

Atazanavir

Cimetidine

Ciprofloxacin

Efavirenz

Enoxacin

Fluoroquinolones

Furafylline

Interferon

Methoxsalen

Mexiletine

Mibefradil

Tacrine

Thiabendazole

Ticlopidine

Vemurafenib

Zileuton

CYP1A2 Potent and Moderate Inducers

Barbiturates

Beta-naphthoflavone

Carbamazepine

Insulin

Methylcholanthrene

Modafinil

Nafcillin

Omeprazole

Primidone

Rifampin

Sensitive and moderately sensitive substrates of CYP2B6, CYP2C8, CYP2C9, and CYP2C19:

Enzyme	Sensitive Substrates	Moderately Sensitive Substrates
CYP2B6	bupropion	efavirenz
CYP2C8	repaglinide	montelukast, pioglitazone, rosiglitazone
CYP2C9	celecoxib	glimepiride, phenytoin, tolbutamide, warfarin
CYP2C19	S-mephenytoin, omeprazole	diazepam, lansoprazole, rabeprazole, voriconazole

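### Exclusion 2 and the antidepressant permission cite only Section 7.4.2, so eligibility misses most of the CYP substrates that Section 7.4.3 bars, and stable bupropion reads as permitted

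*Protocol*

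**What the plan says.** Four parts of the Protocol bear on this.

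- **Eligibility (7.2, criterion 2).** The only criterion that refers to the prohibited-medication lists excludes "Use of prohibited medications as defined in Section 7.4.2".
- **Permission (7.4.1).** Subject to the patient's condition being stable, the permitted list includes "Antidepressants starting at least two months prior to screening except the prohibited medications as described in Section 7.4.2".
- **Ban (7.4.3).** The section opens "The following concomitant medications are neither permitted in the double blind nor the openlabel extension phase of the Study" and then lists "Sensitive and moderately sensitive substrates of the CYP2B6, CYP2C8, CYP2C9, and CYP2C19 enzymes (please see the table below". Appendix III (18.3) reprints the table under "Sensitive and moderately sensitive substrates of CYP2B6, CYP2C8, CYP2C9, and CYP2C19".
- **Eligibility check (8.1.1 and 8.1.2).** At the end of screening, the results of participants who "meet all inclusion and none of the exclusion criteria will be submitted via the ADCS EDC for central confirmation of eligibility". The baseline visit repeats "Verification of Inclusion/Exclusion criteria". Neither step mentions 7.4.3.

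**The concern.** The ban that applies on treatment is wider than the list used to decide who enters. A patient taking, say, celecoxib or pioglitazone meets no listed exclusion, yet is in breach of 7.4.3 at the first dose unless the drug is stopped. For bupropion a site gets opposite answers from two sections a page or two apart.

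If the conflict surfaces only after enrolment, three outcomes are possible: a protocol deviation, withdrawal of a long-term drug, or a decision by the investigator and medical monitor on whether to stop study drug (Section 10).

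Section 1.6 gives a reason to care about bupropion in particular. It reports a maximum 27.0-fold induction of CYP2B6 mRNA and says the study drug may reduce the efficacy of sensitive CYP2B6 substrates; bupropion is the one listed. For the CYP2C8, CYP2C9 and CYP2C19 entries the visible text states no clinical consequence. For those, the point is only that the entry rule and the ban disagree.

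**Working it through.** The plan states no figure to reproduce. The check traces the cross-references and then counts the table entries that no other rule reaches.

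**Step 1: where each rule points.**
- Exclusion 2 points to 7.4.2. No criterion in 7.1 or 7.2 points to 7.4.3.
- The 7.4.1 antidepressant line points to 7.4.2.
- 7.4.2 mentions 7.4.3 once, to limit what investigators may allow in the extension phase. That does not bring the substrate table into 7.4.2.
- The pre-randomisation window in 7.4.3 (14 days or 5 half-lives, whichever is longer) covers CYP1A2 inhibitors and chronic CYP1A2 inducers. It does not cover the substrate table.

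**Step 2: size of the table.** CYP2B6 2 + CYP2C8 4 + CYP2C9 5 + CYP2C19 6 = 17 entries. Named as prohibited in 7.4.2: 0. Warfarin appears there only in the lumbar puncture text.

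**Step 3: entries another rule can reach.**

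| Entry | Other rule | Basis |
|---|---|---|
| Efavirenz | CYP1A2 inhibitor list (Appendix III); HIV exclusion (7.2) | By name |
| Omeprazole | CYP1A2 inducer list (Appendix III), chronic use | By name |
| Diazepam | Long-acting benzodiazepines (7.4.2) | Class reading, assumed |
| Phenytoin | Anticonvulsants (7.4.2), conditional | Class reading, assumed |
| S-mephenytoin | Anticonvulsants (7.4.2), conditional | Class reading, assumed |

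By name: 17 − 2 = 15. Allowing the class readings as well: 15 − 3 = 12.

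**Step 4: what is left.**

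| Enzyme | Entries reached by no other rule | Count |
|---|---|---|
| CYP2B6 | Bupropion | 1 |
| CYP2C8 | Repaglinide, montelukast, pioglitazone, rosiglitazone | 4 |
| CYP2C9 | Celecoxib, glimepiride, tolbutamide, warfarin | 4 |
| CYP2C19 | Lansoprazole, rabeprazole, voriconazole | 3 |

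1 + 4 + 4 + 3 = 12.

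**Step 5: exclusions that might have closed the gap.**
- The serious-illness exclusion concerns conditions, not medicines.
- The diabetes exclusion covers insulin dependence or HbA1c above 8.0%, so a controlled patient on an oral agent in the table passes.
- The anticoagulant text in 7.4.2 and 8.8 keeps warfarin users out of lumbar puncture and the CSF sub-study only, which reads as if they may otherwise take part.

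**Step 6: bupropion.** The antidepressant classes barred in 7.4.2 are tricyclics and monoamine oxidase inhibitors, and bupropion is not among the examples of either. So 7.4.1 read with 7.4.2 permits bupropion started at least two months before screening, and 7.4.3 prohibits it. A late switch is awkward: a replacement antidepressant must itself have started two months before screening, but screening lasts at most 42 days, so a switch made within that period cannot satisfy 7.4.1.

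**The case against.** The strongest reply is that nothing is missing. Section 7.4.3 follows 7.4.2 directly, its heading covers both phases, its substrate ban is unconditional, and Appendix III repeats the table. A prohibition by name would ordinarily override a class permission, so the specific answer on bupropion can be found. Concomitant treatment is recorded at screening and again at baseline before the first dose, with central confirmation in between. A drug barred only on treatment need not be a screening exclusion, because a patient could be switched before dosing and comply with both rules. It can also be said that citing 7.4.3 in exclusion 2 brings in rules with different timing.

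Much of this stands. The ban is in the protocol, a careful site or the central reviewers may catch the conflict, and no enrolment error has been shown. What does not follow is that the text is consistent. Both eligibility steps are described against the listed criteria alone. For bupropion, nothing states which section governs. The timing point does not defeat the change, because a criterion that refers to medicines as defined in each section carries that section's own timing.

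The count is also open to challenge. Section 7.4.2 includes an open-ended class beginning "Hepatotoxic drugs (e.g. allopurinol, methyldopa, sulfasalazine) which may increase the" and ending with the risk of liver toxicity. A site that read some of the 12 into that class would get a lower number; the documents do not enumerate it.

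**Conclusion.** The concern holds. The entry rule and the antidepressant permission both stop at 7.4.2, while the ban on these substrates sits in 7.4.3. Of 17 table entries, none is named as prohibited in 7.4.2, and about 12 are reached by no other rule. The figure is 15 without the three class readings, which rest on general pharmacology rather than document text, and could fall below 12 under a broad reading of the hepatotoxic class. One entry, bupropion, is directly contradictory, and it is the only one of the 12 for which Section 1.6 states a concern.

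The impact is modest. The consequences are avoidable deviations and late medication decisions in an unknown number of participants. Sample size, power, type I error, the estimand and the planned analyses do not change.

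**What to change.** Make two changes of wording at the next amendment:

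1. In 7.2, let exclusion 2 refer to prohibited medications as defined in Sections 7.4.2 and 7.4.3.
2. In 7.4.1, let the exception in the antidepressant line refer to the same two sections, so that bupropion is clearly excepted.

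Neither a washout interval for the substrates nor any change to the lumbar puncture text is needed to remove the inconsistency.

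The cost is a few more screen failures or medication switches during screening, all among patients whom 7.4.3 already bars from treatment while on these drugs. A switch may still be needed, but it would be settled before randomisation.
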